### **7.3 Adverse Events and Serious Adverse Events**

Definition of adverse events and unanticipated problem involving risks to subjects or others (UPIRSO): The following definitions of adverse events are included in the NCCIH toolbox DSMP information and we have adopted these same definitions for use in monitoring the safety of participants in the proposed project. We will report all AEs, SAEs, and UPIRSOs to the NCCIH and VA Central IRB as required.

Adverse event (AE): An AE is defined as any untoward physical or psychological occurrence in a human participant taking part in research. An AE can be any

unfavorable or unintended event including abnormal laboratory finding, symptom or disease associated with the research or the use of a medical investigational test article. An AE does not necessarily have to have a causal relationship with the research, or any risk associated with the research or the research intervention, or the assessment.

Serious Adverse Event (SAE): A serious adverse event (SAE) is one that meets one or more of the following criteria:

- Results in death
- Is life-threatening (places the subject at immediate risk of death from the event as it occurred)
- Results in inpatient hospitalization or prolongation of existing hospitalization
- Results in a persistent or significant disability or incapacity
- Results in a congenital anomaly or birth defect

An important medical event that may not result in death, be life threatening, or require hospitalization may be considered an SAE when, based upon appropriate medical judgment, the event may jeopardize the subject and may require medical or surgical intervention to prevent one of the outcomes listed in this definition.

Unexpected Adverse Event (UAE): An UAE is any adverse event and/or reaction, the specificity or severity of which is not consistent with the informed consent, current investigator brochure or product labeling. Further, it is not consistent with the risk information described in the general investigational plan or proposal.

Unanticipated problem involving risks to subjects or others (UPIRSO): The Office for Human Research Protections (OHRP) considers unanticipated problems involving risks to subjects or others to include, in general, any incident, experience, or outcome that meets all of the following criteria:

- Unexpected in terms of nature, severity, or frequency given (a) the research procedures that are described in the protocol-related documents, such as the IRB-approved research protocol and informed consent document; and (b) the characteristics of the subject population being studied;
- Related or possibly related to participation in the research (“possibly related” means there is a reasonable possibility that the incident, experience, or outcome may have been caused by the procedures involved in the research); and
- Suggests that the research places subjects or others at a greater risk of harm (including physical, psychological, economic, or social harm) than was previously known or recognized.

Time Period and Frequency for Event Assessment and Follow-up

Unanticipated problems will be recorded in the data collection system throughout the study. The PI will record all reportable events with start dates occurring any time after informed consent is obtained until 7 (for non-serious AEs) or 30 days (for SAEs) after the last day of study participation. Participants in the COPES (IVR-based CBT-CP) intervention will be asked to report any AEs weekly. At each follow-up assessment point study staff will examine participant electronic health records for the occurrence of AE/SAEs since the last assessment. Events will be followed for outcome information until resolution or stabilization.

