## **Interventions and Duration**

### COPES (IVR-CBT-CP)

Overview. COPES (IVR-CBT-CP) is a 10-week, IVR-facilitated program of CBT for chronic pain. The primary components of the intervention include: 1) a self-help handbook containing the rationale and instructions for using eight pain self-management skills, and their corresponding weekly skill practice goals; 2) a pedometer-facilitated walking program; 3) daily, automated IVR calls to collect patient-reported pain intensity and pain interference, sleep quality, pedometer-measured step count, and adherence to the pain coping skill practice ratings; and 4) weekly, two to four minute pre-recorded, personalized therapist messages based on participant IVR-reported data. The COPES IVR system provides participants the ability to automatically connect to the Veteran Crisis Line during any call. In this study, COPES will be centrally delivered from the VA Connecticut site. Participants will be given up to 14 weeks to complete treatment to allow for missed sessions (vacations, illness).

Intake and materials. Each weekly IVR module will feature a single self-management skill (e.g., paced physical activity, stretching, or relaxation) reinforced via a companion chapter in the patient handbook. The handbook, developed for the initial COPEs efficacy trial and refined prior to the ongoing COPEs implementation trial, is written at the 6th grade reading level and features design strategies to enhance engagement and readability. The manual will assign a specific goal each week that promotes practice of the module's coping skill (e.g., practice deep breathing for 5 minutes each day this week). The participant will be instructed to practice that week's skill each day of the week and report via daily IVR assessment their daily skill practice completion (0=not at all completed to 10=totally completed). Participants will have access to a patient handbook through the COPEs website. If patients do not have Internet access the handbook will be mailed to them. Participants will also be mailed an Omron Go Smart Model HJ-112 pocket pedometer to facilitate their participation in the walking portion of the treatment.

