Daily IVR assessment calls. Prior to treatment and after the study baseline evaluation, participants will undergo daily IVR assessment of pain intensity, pain interference, pedometer-measured step counts, sleep quality, and sleep duration for seven days to establish a baseline of function. After the baseline period, participants will continue to receive daily calls for the duration of the 10-week treatment. During the treatment period two additional questions regarding pain skill practice and progress toward the weekly meaningful activity goal will be included. Patient-reported data collected on the IVR assessment calls will form the basis for therapist feedback. Calls will continue through an immediate one-week post-treatment assessment period. COPEs participants will receive automated calls each evening between 6pm and 10pm at a time pre-selected by the patient to ensure that each call captures the full 24-hour reporting period. On evenings when participants miss their scheduled call, the IVR system will call again 2 additional times. Alternatively, participants may initiate a call into the system themselves. Study staff automatically receive alerts when participants do not respond to their first call or do not respond to two consecutive daily calls. During the IVR call, participants may directly access the VHA suicide crisis line by pressing 777# from the main menu or they may leave a message for their COPEs therapist.

Pedometer-Assisted Graduated Walking Program. The COPEs intervention includes a graduated walking component supported by daily reporting of pedometer-measured step counts. Participants will report their daily step count during the daily IVR assessment. Each week, a new daily step target will be calculated by adding 10% to the prior week's average daily step count and that target will be communicated to participants during the weekly personalized, asynchronous therapist feedback.

Meaningful Activity Goal. Participants will learn the basics of goal setting using the SMART (specific, measurable, achievable, relevant, and timely) framework in the introductory handbook module. They will be asked to generate a weekly meaningful activity goal using this format.

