### **7.5 Follow-up for Adverse Events**

During the follow-up assessment points, study staff will retrospectively examine participants' electronic medical record to determine if AEs, SAEs, or UPIRSOs have occurred and report to the cIRB, NCCIH, the IC as outlined above

In the COPES (IVR-CBT-CP) condition, participants will be monitored weekly for the full 11 weeks of the study. All participants will be monitored using automated IVR calls at multiple study timepoints (baseline, 1 4, 6, and 12 months). Safety data will only be retrospectively collected during post follow up assessments.

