#### **10.3.4 Protocol Deviations**

Meetings of the larger research group (PI, staff at engaged sites, and the VA Connecticut research team) will allow us to detect deviations from the IRB-approved protocol. No recruiting, consenting, randomizing, or assessment will occur at the non-engaged sites so there is no need to monitor their activities for compliance.

COPES and CBT-CP are minimal risk interventions and CBT-CP and its variants are considered standard of care for chronic pain. Based on previous experience with this study population, we added diabetic foot ulcer as an exclusion criterion from the study. COPES+UC participants will be centrally treated at VACHS. Regular meetings will be held between the PI and study staff members who will be delivering the intervention locally from VACHS. Additionally, for the CBT-CP+UC participants, regular meetings will be held between the PI and each site liaison. During these meetings staff will convey any issues or adverse events (AEs), serious adverse events (SAEs), unexpected adverse events (UAEs), or unanticipated problems involving risks to participants or others (UPIRSOs), that may occur at these sites and report to the cIRB within 5 days, as necessary, or at continuing review for AEs that do not meet criteria for reporting within 5 days.

During follow up (4, 6 & 12), the study coordinator will retrospectively examine participants' electronic medical record to determine if AEs, SAEs, or UPIRSOs have occurred and report to the cIRB within 5 days, as necessary or at continuing review for AEs that do not meet criteria for reporting within 5 days.

In the COPES+UC condition, participants will be monitored weekly for the full 11 weeks of the study. All participants will be monitored using automated IVR calls at multiple study timepoints (baseline, 1, 4, 6, and 12 months). Safety data will only be retrospectively collected during post follow up assessments.

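### No scheduled safety review reaches the plan's own 7- and 30-day windows after month 12, and the 11 weeks of weekly COPES monitoring are not reconciled with treatment of up to 14 weeks

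*Combined protocol and SAP*

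**What the plan says.** **Recording period.** Section 7.3 makes the investigator responsible for recording events that start after consent and "until 7 (for non-serious AEs) or 30 days (for SAEs) after the last day of study participation".

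**How events are found.** The same section states: "At each follow-up assessment point study staff will examine participant electronic health records for the occurrence of AE/SAEs since the last assessment". Section 10.3.4 gives the time points: "During follow up (4, 6 & 12), the study coordinator will retrospectively examine participants' electronic medical record". The schedule in Section 6.1 marks adverse events at months 4, 6 and 12 only, and Section 6.2.5 makes the final visit the same as the other follow-ups. Section 7.5 adds, and Section 10.3.4 repeats: "Safety data will only be retrospectively collected during post follow up assessments". The reporting tables in Sections 7 and 7.4 place AE assessment at the end of treatment and at later assessment points, and name nothing after month 12.

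**Weekly monitoring in the COPES arm.** Section 7.5, repeated in Section 10.3.4, says "participants will be monitored weekly for the full 11 weeks of the study". The COPES descriptions in the Précis and Section 5.1 say "Participants will be given up to 14 weeks to complete treatment to allow for missed sessions" and "Calls will continue through an immediate one-week post-treatment assessment period". Section 7.3 asks COPES participants to report AEs weekly and gives no end date.

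**The concern.** A recording period means something only if a collection step reaches its end. Here the period extends past the last assessment, but every scheduled review looks back from an assessment. An SAE that starts two weeks after month 12 is recordable under Section 7.3, and no planned step would find it. The Annual Report must list AEs and judge whether their rates match expectation, so the end of each participant's record would be incomplete in a way that readers of the report could not see.

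The 11-week figure raises a smaller question. A COPES participant who uses the time allowed for missed sessions is still in treatment after week 11. Section 2.2 says that most related AEs in the earlier efficacy trial were small increases in pain from exercise. Events of that kind may never reach a chart, so weekly self-report is the route most likely to pick them up.

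**Working it through.** **1. Recording windows against the last review**

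Inputs: windows of 7 and 30 days (7.3); last review at month 12 (6.1, 10.3.4); assessment window from 1 week before to one month after the planned date (6.2.4); assessments over 12 months (Section 3). One month = 365.25/12 = 30.44 days, so month 12 is day 365. The last day of participation is taken as the day of the month-12 assessment.

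| Month-12 assessment | Done on day (look-back ends) | AE window ends (+7) | SAE window ends (+30) |
|---|---|---|---|
| Window opens | 358 | 365 | 388 |
| Planned date | 365 | 372 | 395 |
| Window closes | 396 | 403 | 426 |

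In every row 7 and 30 days remain uncovered, because a late assessment moves the last day of participation with it. The gap would close only if the last day were pinned to the planned date (365 + 30 = 395) and the review were held to the end of the window (day 396). The plan does not say this.

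**2. Size of the uncovered period**

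The documents give no SAE rate for this trial, so the rates here are assumptions.

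- Person-time if all 764 participants reach month 12: 764 × 30/365 = 62.8 person-years.
- SAEs at 0.1, 0.2 and 0.3 per person-year: 6.3, 12.6 and 18.8.
- With the 20% attrition of Section 9.2: 764 × 0.8 = 611; 611 × 30/365 = 50.2 person-years; 5.0 to 15.1 SAEs at 0.1 to 0.3.

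**3. The 11 weeks**

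- The plan's figure reproduces as 10 treatment weeks + 1 post-treatment call week = 11. This derivation is inferred; the documents do not give it.
- Adding the seven days of calls before treatment: 1 + 10 + 1 = 12 weeks for a participant who is on time.
- Against the allowance: 14 − 11 = 3 weeks. With the post-treatment call week: (14 + 1) − 11 = 4 weeks.

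**4. Does another collection step reach those weeks?**

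- Month 4 = 4 × 30.44 = 121.8 days = week 17.4. Its window opens one week earlier, at week 16.4.
- The end of week 14 is 16.4 − 14 = 2.4 weeks before the earliest month-4 review and 17.4 − 14 = 3.4 weeks before the planned one. The end of week 15 is 1.4 weeks before the earliest.
- The month-1 assessment is at week 4.35, and its window closes at week 8.7. Weeks 12 to 15 therefore lie after the previous assessment and inside the month-4 look-back, in both arms.

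**The case against.** **The key term is undefined.** If the last day of participation meant the end of the intervention, the month-12 review would cover both windows. This stands as a limit on certainty. Month 12 remains the more natural reading, since participants complete assessments for 12 months, and the ambiguity is itself a reason to edit.

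**There may be another route.** Section 10.3.4 describes regular meetings with site liaisons at which AEs and SAEs are conveyed. None is tied to the period after month 12, and Section 7.4 says communication from local site personnel is not needed, so the two sections conflict. Section 7.3 also follows events to resolution, but that applies to events already found.

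**The count is soft.** It rests on assumed rates and on every participant reaching month 12. Section 8 keeps participants withdrawn from the intervention in follow-up; if their participation is held to end earlier, their 30 days fall inside a later review. The earlier trial reported only two SAEs, judged unrelated. This objection stands: 6 to 19 is a conditional upper range, not a forecast of missed events.

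**The consequence is slight.** The uncovered days come about eight months after COPES treatment ends, and Section 10.3.5 describes a minimal-risk trial that needs no intensive safety monitoring. This also stands.

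**On the 11 weeks**, a reader might infer that safety collection in the COPES arm stops while participants are still being treated. The documents do not support that. Weekly reporting in Section 7.3 has no end date, calls run to one week after treatment, and the month-4 review looks back over the weeks in question. The 11 weeks may simply describe the nominal course. A reader might also add the pre-treatment week to reach 1 + 14 + 1 = 16 weeks, but Section 8 counts the 14 weeks from baseline (stated for those who re-enroll), which gives 15. Even week 16 would end 0.4 weeks before the earliest month-4 review.

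**Conclusion.** The main point holds. When participation ends at the month-12 assessment, no scheduled collection reaches the 7-day and 30-day windows that the plan sets for itself. This assumes that month 12 is the last day of participation. In size it is at most about 6 to 19 SAEs, if all 764 participants reach month 12 and the rate is 0.1 to 0.3 per person-year; most would probably be unrelated to treatment. The documents do not show that any particular number will be missed. No efficacy endpoint, stopping rule or comparison between arms is shown to change.

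The second point holds only as a wording conflict. Eleven weeks of weekly monitoring are not reconciled with treatment of up to 14 weeks plus a call week. The most that could be lost is weekly self-report, over 3 or 4 weeks, of mild events that never reach the chart, and only if the 11 weeks are applied as a hard stop. Both points merit a correction, and neither is a serious safety failure.

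**What to change.** 1. Define the last day of study participation in Section 7.3, including for participants who leave before month 12.
2. Schedule the final record-based safety review at least 30 days after that day, and show it in Sections 6.1, 7.5 and 10.3.4. For a month-12 assessment on its planned date this is day 395 or later. The review needs no participant contact; the cost is about one month's later closure for the last participants.
3. Reconcile the 11-week wording in Sections 7.5 and 10.3.4 with the 14-week allowance and with the open-ended weekly reporting in Section 7.3. One way is to state that the weekly AE question continues for as long as the participant's own COPES calls continue. This is a wording change that uses calls already planned and leaves the treatment allowance alone.
4. Settle whether site-liaison meetings are a source of safety reports, since Sections 7.4 and 10.3.4 disagree.

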were also provided a pedometer and instructed to increase their daily step counts by 10% each week. All participants received brief automatic nightly IVR calls to assess pedometer-measured step-counts and other pain-related outcomes. At 12 weeks post enrollment, statistically significant improvements in physical functioning, sleep quality, and physical quality of life relative to baseline occurred in both treatments, with no advantage for either treatment (Figure 1). Post-treatment, 33% of subjects receiving in-person CBT reported clinically meaningful improvement in pain intensity of at least 30%, compared to 19% receiving IVR-CBT ( $p=0.19$ ). For physical functioning/disability, 35% of participants in in-person CBT and 45% in IVR-CBT reported a reduction of at least 30% ( $p=0.43$ ). Additionally, the “IVR CBT” participants reported step count increases that were comparable to the increases observed in “in-person CBT.” Overall, across all participants, an average increase of 2,072 steps per day was observed from baseline to follow-up; this equates to an increase of approximately one mile of walking per day. Additionally, IVR-CBT patients received 2.3 (95% CI: 1.0, 3.6) more weeks of treatment than patients attending in-person sessions, and patients were equally satisfied with IVR and in-person therapy. Finally, participants were proactively assessed each week for study-related adverse events. Forty-six participants experienced 92 related and unrelated AEs (COPES=40, In-person CBT=52). Most related AEs were small increases in pain from exercise. The number of AEs was not significantly different by treatment group ( $p=0.44$ ). Only two serious AEs were reported, but judged by the IRB to be unrelated to study participation.

**Figure 1. Pain Intensity (left panel) and daily steps (right panel) reported among VHA patients with back pain randomized to in-person CBT (red line) vs. IVR CBT (blue line).**

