## 7. SAFETY ASSESSMENTS

Study progress and safety will be reviewed monthly. Progress reports, including patient recruitment, retention/attrition, and adverse events (AEs) will be provided to the Independent Monitor(s) semi-annually. An Annual Report will be compiled and will include a list and summary of AEs. In addition, the Annual Report will address (1) whether AE rates are consistent with pre-study assumptions; (2) reason for dropouts from the study; (3) whether all participants met entry criteria; (4) whether continuation of the study is justified on the basis that additional data are needed to accomplish the stated aims of the study; and (5) conditions whereby the study might be terminated prematurely. The Annual Report will be sent to the Independent Monitor(s) and will be forwarded to the IRB and NCCIH. The IRB and other applicable recipients will review progress of this study on an annual basis. The IRB and NCCIH Program Officials will receive copies of all study monitoring/audit or inspection reports within 14 day of PI receipt.

Table of reporting activities

Data type	Frequency of review	Reviewer
Subject accrual (including compliance with protocol enrollment criteria)	Monthly	PI, Internal QA Reviewer
	Semi-annually	Independent Monitor(s)
Status of all enrolled subjects, as of date of reporting	Monthly	PI, Internal QA Reviewer
	Semi-annually	Independent Monitor(s)
Data entry quality control checks on 10% of charts	Weekly	QA Reviewer
Adherence data regarding study visits and intervention	A monthly report will be prepared containing information on those assessed.  Participants will be assessed at the end of treatment and subsequent assessment points	PI, Internal QA Reviewer
	Semi-annually	Independent Monitor(s)
AEs and rates	A monthly report will be prepared containing	PI, Internal QA Reviewer

	information on those assessed. Participants will be assessed at the end of treatment and subsequent assessment points	
	Semi-annually	Independent Monitor(s)
	Annually	NCCIH, FDA (If Applicable)
SAEs (unexpected and related)	Per occurrence	PI, Independent Monitor (s) NIH/NCCIH, FDA (if applicable)
SAEs (expected or unrelated)	Per Occurrence	PI, Internal QA Reviewer
	Annually	Independent Monitor (s), NIH/NCCIH
Unanticipated Problems	Monthly	PI, Internal QA Reviewer
	Per Policy	IRB, FDA (if applicable)

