## 7.1 Specification of Safety Parameters

The interventions are minimal risk and in fact are two forms of guideline recommended non-pharmacological care for chronic pain already provided in the VHA system. Adverse events will be reported by patients via the IVR system and/or medical records review.

COPES (IVR CBT-CP) and synchronous CBT-CP are minimal risk interventions and CBT-CP and its variants are considered standard of care for chronic pain. COPES (IVR-CBT-CP) participants will be centrally treated at VACHS. Regular meetings will be held between the PI and study staff members who will be delivering the intervention locally from VACHS. Additionally, for the synchronous CBT-CP participants study staff will review participant's electronic health records to identify AEs and UPIRSO.

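### Non-serious adverse events are asked about weekly only in COPES, so by-arm AE rates are not comparable and lean towards more events in COPES

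*Combined protocol and SAP*

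**What the plan says.** The weekly question is set in section 7.3 for one arm: "Participants in the COPES (IVR-based CBT-CP) intervention will be asked to report any AEs weekly". Section 7.5 repeats it for COPES alone: "participants will be monitored weekly for the full 11 weeks of the study". Section 10.3.4 says the same.

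For the synchronous arm, section 7.1 has study staff use participants' "electronic health records to identify AEs and UPIRSO".

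Other sources are not tied to an arm. Section 7.1 says of the trial as a whole: "Adverse events will be reported by patients via the IVR system and/or medical records review". Section 7.3 says: "At each follow-up assessment point study staff will examine participant electronic health records for the occurrence of AE/SAEs since the last assessment". The schedule in section 6.1 has an adverse event row at months 4, 6 and 12 for everyone. Section 7.5 has automated calls to all participants at baseline and at months 1, 4, 6 and 12.

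Under the reporting tables in sections 7 and 7.4, AE rates go monthly to the investigator and the internal reviewer, semi-annually to the independent monitors and annually to NCCIH. The annual report must address "whether AE rates are consistent with pre-study assumptions". Section 7.2 has analysis of safety parameters in its title but deals only with suicide risk, and section 9.6 contains no AE analysis.

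**The concern.** An AE rate reflects how often events happen and how hard one looks for them. Here one arm is looked at harder during treatment, and nothing keeps the extra source out of the rates by arm. The events most exposed are mild and non-serious, which a patient may mention when asked but which need not appear in a medical record. Section 2.2 reports that most related events in the earlier COPES trial were small increases in pain from exercise, which is that kind of event.

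The earlier trial did not have this problem as described: "participants were proactively assessed each week for study-related adverse events", with no split by arm.

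At stake is what the monitors and NCCIH can read from the rates. COPES could look less safe than it is, or mild events in the synchronous arm could go unseen. A genuine signal in COPES could also be dismissed as a product of asking more often.

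**Working it through.** The plan states no AE rate, capture probability or AE comparison for this trial, so there is no figure to reproduce. The check sets the sources side by side and then asks how large the distortion could be.

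**1. Sources by arm**

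| Source | COPES | Synchronous | Section |
|---|---|---|---|
| Weekly question, 11 weeks | yes | no | 7.3, 7.5, 10.3.4 |
| Record review at follow-up | yes | yes | 7.3, 10.3.4; 7.1 names it for synchronous |
| AE row at months 4, 6, 12 | yes | yes | 6.1 |
| Automated calls at baseline, 1, 4, 6, 12 months | yes | yes | 7.5, 10.3.4 (AE content not stated) |
| Meetings with the investigator | with COPES treatment staff | with site liaisons | 10.3.4; but 7.4 says local communication is not needed |

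The weekly question is the only patient-report source present in one arm and absent in the other.

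**2. Occasions on which a patient is asked**

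- If the section 6.1 AE row is a question to the patient: COPES 11 + 3 = 14, synchronous 3.
- If the month 1 call also counts: 11 + 4 = 15 against 4.
- Section 10.3.4 describes the month 4, 6 and 12 activity as record review, and the outcome measures listed in section 6.2.2 include no AE item. If the row means record review only, synchronous patients may never be asked directly. The plan should say which it is.

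**3. Effect on the ratio of rates**

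Let q be the share of events found by the shared sources, relative to weekly asking. Assume equal true rates, constant over 52 weeks. The range q = 0.2 to 0.5 is an assumption with no source in the documents.

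- Within the 11 weeks: ratio = 1/q. At q = 0.5 this is 2; at q = 0.2 it is 5.
- Over 52 weeks, with both arms at q for the other 41 weeks: ratio = [11/52 + (41/52)q]/q.
  - q = 0.5: (0.212 + 0.394)/0.5 = 1.21.
  - q = 0.2: (0.212 + 0.158)/0.2 = 1.85 (1.846 before rounding), or about 1.8.
- At q = 1 both ratios are 1 and there is no distortion.

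**4. In participants**

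Take 382 per arm (section 9.2) and assume a true risk of 20% in both arms and a COPES capture of 0.9.

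- Synchronous capture 0.7: 382 × 0.2 × 0.9 = 68.8 against 382 × 0.2 × 0.7 = 53.5 participants with an event; ratio 1.29.
- Synchronous capture 0.5: 68.8 against 38.2; ratio 1.80.

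Both ratios lie in the 12-month range of step 3. If someone tested these differences at the 5% level, the chance of nominal significance with no true difference would be about 33% and 89% respectively.

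**5. If the true ratio is not 1**

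The earlier trial recorded 40 events in COPES and 52 in person (section 2.2). With arms of similar size (an assumption), the ratio is 40/52 = 0.77. An excess in COPES would then appear only if the capture ratio exceeded 52/40 = 1.30. Capture of 0.9 against 0.7 gives 0.77 × 1.29 = 0.99, no excess; 0.9 against 0.5 gives 0.77 × 1.80 = 1.38.

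**The case against.** The strongest reply is that the arms share more than the weekly question suggests. Records are read in both arms, the AE row covers both, and synchronous sessions are all documented in the health record (section 5.4), so mild events may well appear in session notes. No between-arm AE test is planned, and the annual report compares rates with pre-study assumptions, not between arms. The asymmetry also follows from a deliberate pragmatic choice to leave synchronous care as usual practice, without study staff at the sites. All of this stands, and it limits the problem to descriptive reporting of non-serious events. It does not remove it, because descriptive rates are what monitors see and no rule separates the sources.

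A reader might infer more than the documents support:

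- **That COPES will show an excess and that it will be an artefact.** Step 5 shows that an excess need not appear. If one does, it may be real: in this trial the pedometer walking programme is described for COPES (sections 4.3 and 5.1).
- **That synchronous events come from charts alone.** The shared sources above say otherwise.
- **That the trial-wide ratio is 2 to 5.** That range applies only inside the asking window and rests on an assumed q.
- **That mild events rarely reach a chart.** No passage says how often they do.
- **That the earlier trial's counts are the pre-study assumptions.** No passage says so.
- **That 11 weeks of monitoring contradicts the call schedule.** Ten treatment weeks plus one post-treatment week make 11; the seven-day run-in comes before treatment. At most, monitoring is unclear for patients who use the allowance of up to 14 weeks.

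**Conclusion.** The concern holds for non-serious events in descriptive rates by arm. Ascertainment is more intensive in COPES, the bias is towards more events there, and the plan has no rule to contain it. Serious events such as hospitalisation or death should be much less affected, because record review covers both arms.

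The size cannot be fixed from the documents. The 12-month distortion of about 1.2 to 1.8 rests on an assumed q of 0.2 to 0.5, equal and constant true rates, and equal yield from the shared sources in both arms. The lasting difficulty is confounding: a true effect of the walking programme and the effect of weekly asking point the same way, and pooled rates cannot separate them.

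Two conflicts in the text add to the uncertainty. Sections 7.5 and 10.3.4 say that safety data are gathered only in retrospect after follow-up assessments, against the weekly asking in section 7.3. Section 10.3.4 uses meetings with site liaisons to pass on AEs, while section 7.4 says that communication from local staff is not needed.

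**What to change.** In sections 7.2 and 7.5:

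- Record the source of each AE (weekly COPES report, record review, month 4, 6 or 12 assessment, other).
- State that any between-arm AE table uses only sources common to both arms: record review and the month 4, 6 and 12 assessments.
- List events known only from weekly COPES reports in a separate table, and keep reporting them in full for safety oversight.
- Say whether the month 4, 6 and 12 AE row is a question to the patient, a record review or both.
- Reconcile weekly asking with the retrospective-only sentences, and section 10.3.4 with section 7.4 on the liaison route.

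The cost is one field on the AE record, back-filled for events already entered, and some table wording. No new data collection is needed. The downside is that between-arm tables will count fewer mild COPES events, which is why the separate listing matters. The shared sources may still not yield equally, since synchronous session notes sit in the record under review; a footnote to the table should say so.
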